#### **RST Program and Telehealth/In-Person Visits:**

**RST Program:** Enrolled CS patients will undergo a preoperative RST program immediately following Research Evaluation 1 (preoperative, pre-RST) with a targeted duration of 4-weeks that will vary dependent upon available time between the patients preop and surgery schedule. RST will be completed from the patients' home with portable expiratory and inspiratory training devices our lab has previously used: the EMST-150 or the EMST75 Lite and the IA-150 devices (Aspire Products, Gainesville, Florida, Fig. 4). The EMST 75 Lite has a resistance range of 0-75cm H2O and the EMST-150 and IA-150 devices have a resistance range of 30 to 150cm H2O and represent spring-loaded pressure threshold devices (Fig. 4). For completion of exercises, each device will be set to a patient's individualized 70% MEP or MIP. Following the baseline evaluation, trainers will be calibrated to the appropriate setting, and the patient will be trained on how to perform exercises. Additionally, they will be provided with a training manual that includes detailed instructions and photographs to provide reinforcement of the initial training session.

**Fig. 4: Respiratory training devices.** Images from <https://emst150.com/product/emst150-ia150-inspiratory-adapter-bundled-combo/> (Aspire Products, <https://emst150.com/>)

Participants will need to demonstrate proficiency in performing both the expiratory muscle strength training (EMST) and inspiratory muscle strength training (IMST) exercise prior to leaving the clinic and will be given a training log to record their daily sessions and a telehealth appointment card with weekly meeting dates and instructions for how to access the secure telehealth portal (a secure version of Zoom).

The RST protocol will be the previously utilized “Rule of 5’s” that includes training 5 days per week and performing 5 sets of 5 reps (i.e., 25 repetitions) for both expiratory and inspiratory muscle strength training. Thus, a total of 50 repetitions (25 IMST, 25 EMST) will be performed by enrolled participants. CS patients will be instructed to breathe in (IMST) or out (EMST) for several seconds until the valve audibly releases. Between repetitions, CS patients will be instructed to rest 10-15 seconds before the next repetition. After each set, CS patients will be instructed to rest for one minute before completing the next set. Repetitions will be recorded in a training log provided to the CS patients to track adherence and the quality of repetitions will be monitored during weekly telehealth sessions.

Telehealth Sessions: CS patients will complete one-five training sessions per week via telehealth with a research speech-language pathologist to ensure patients are using correct form and technique, to complete a safety and adverse event check, to answer any questions patients may have, and to assist with adherence issues. The number of telehealth visits per week will be determined based on individual patient factors including 1) patient performance of the RST program, and 2) patient requests for additional training/clarification. The research speech-language pathologist may recommend up to 5 telehealth visits per week and/or patients may request additional telehealth sessions (up to 5 per week) if they have questions or require additional support to perform the RST exercises correctly. EMST/IMST devices will also be recalibrated weekly using the Borg Category Ratio 10 Scale to measure perceived effort of the RST exercise equal to 70% MEP/MIP (Borg scale score of 7/10). The Borg Category Ratio Scale has been used in the limb literature and demonstrated accuracy in measuring %repetition max (RM). For example, a score of 2 is approximately 20% of a RM and a score of 7 is approximately 70% of a RM. To ensure patient privacy, telehealth sessions will take place in a private room using a UF secure telehealth platform (a secure version of Zoom). Attendance for weekly telehealth sessions will be tracked.

In-Person Visit: CS patients will also have one in-person visit within participants’ homes or the research laboratory (DG-136) with a study team member at the mid-point of the RST program to ensure patients are using correct form and technique, to complete a safety and adverse event check, to answer any questions patients may have, and to assist with adherence issues. EMST/IMST devices will also be recalibrated by retesting MEP and MIP and setting the devices to 70%. LCADL ratings and functional speech measures (bamboo passage) will also be obtained.

Training Logs: CS patients will fill out daily training logs to track RST repetitions (adherence) and to note any adverse events related to RST. The PI will calculate the total number of repetitions completed by each participant at the conclusion of the training period.

Aim 1 Outcomes will include patient adherence to RST, attendance at telehealth/in-person treatment sessions, and adverse events associated with RST. We hypothesize that RST will be safe, well-tolerated, and feasible in CS patients as measured by high adherence to RST, attendance at all telehealth/in-person sessions, and no reported adverse events.

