**Sample size justification:** Given that this is a pilot study to determine primarily safety and feasibility data to determine whether a large-scale clinical trial is warranted, a justification based on statistical power to test hypotheses strictly at the  $\alpha=0.05$  level is not appropriate. The findings from this exploratory study will be used to perform future sample size and power calculations to examine the safety, feasibility, and impact of preoperative RST in a larger cohort of CS patients.

**Statistical analyses:** Descriptive statistics, magnitudes of estimates, and spaghetti and needle plots that visualize individual-level data across time points will first be utilized to summarize data in this small cohort and prior to performing conventional analyses and hypothesis testing.

**Aim 1:** Attendance, RST adherence, and adverse events will be summarized descriptively with frequency counts and percentages.

**Aim 2:** Descriptive statistics and an appropriate repeated measures analysis based on the distribution of data will be used to evaluate potential change in FVC, MEP, MIP, voluntary cough peak expiratory flow, and cough spirometry metrics, speech rate, number of pauses, duration of pauses, LCADL ratings across time points (pre-RST vs. post-RST).

**Aim 3:** Descriptive statistics will be used to summarize swallowing safety profiles postoperatively (frequency histogram, mean, mode, range of PAS, DIGEST, NZSS, YRS scores), and logistic regression will be used to compare swallowing safety and efficiency across timepoints. Postoperative rates of pneumonia, reintubation, duration of intubation, intubation fast track status, any related respiratory therapy outcomes, 30-day readmission, mortality, and time to oral intake/hospital LOS, etc. will be summarized descriptively (frequency counts, %) and compared to our historical data set in CS patients.

**Data Management and Quality Control:** Research Electronic Data Capture (REDCap) will be used to enter and store data for the current study, which is a secure web-based application hosted at the University of Florida. REDCap has a variety of features that streamline data entry and processing including the ability to download and export data directly to commonly used statistical analyses software. The ARC lab has successfully used REDCap for data collection, storage, and analyses for other research studies

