**Table 9. Summary of Study Outcomes and analyses by specific aim.**

AIM:		STUDY VISIT	OUTCOMES:	ANALYSIS:
Aim 1	Feasibility & safety of RST	RST at-home program, Telehealth appts/In-person visit	# RST reps completed /# prescribed, # sessions completed /# scheduled, Adverse events.	Frequency counts, percentages.
Aim 2	Physiologic impact of RST	Research Exam 1, Research Exam 2	FVC, MEP, MIP, Cough PEF, Cough spirometry metrics, Speech rate, number of pauses, duration of pauses, LCADL ratings	Descriptive statistics, Repeated measures ANOVA (or non-parametric dep' distribution)
Aim 3	Postoperative health-related outcomes	Research Exam 3, 90-days postoperatively	Swallowing safety and efficiency, intubation duration, pneumonia, reintubation, 30-day readmission, 90-day mortality, time to oral intake, hospital LOS (ICU and total), relevant respiratory therapy outcomes	Frequency counts, Percentages, Logistic regression.

**Data Safety Monitoring Plan (DSMP):** [name] will provide medical oversight for this study and we will utilize standard IRB oversight to monitor any adverse events or protocol deviations. The UF-IRB will review the human subject protocol and will monitor the quality of research occurring under the approved protocol during annual continuing reviews. The IRB must approve the protocol annually, as the study progresses. Data safety monitoring will occur during weekly meetings to review Adverse Events (AE) and Protocol Deviation Logs with the PI and study team. In the event of an unanticipated adverse response, the participant's physician will be immediately notified, and the participant will be seen for a complete evaluation. Data, adverse events, and individual subject safety are monitored throughout each subject's evaluation as well as during weekly laboratory meetings with the PI and study team that adhere to the UF IRB regulations for reporting of AE's and protocol deviations.

**Potential Risks:** All participants will be required to pass a COVID-19 Test (i.e., COVID-19 negative) that is performed as standard of care in all surgical patients prior to being allowed to participate in this study. Thus, the risk for personal working on this project, in addition to potential cross contamination of equipment will not be a factor.

The following risks will be disclosed to all participants prior to obtaining their consent to participate:

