- A Fiberoptic Endoscopic Evaluation of Swallowing (FEES) can result in discomfort, gagging or vomiting. Although extremely rare other complications that have been reported can include vasovagal episode (0.06%

reported incidence), laryngospasms (0.03% reported incidence), or epistaxis (0.3% reported incidence). The reported incidences of these adverse reactions to FEES are based on published reports in 6,000 patients.

- b) Aspiration (material in trachea) is always a possible risk during the FEES exam, as the test is intended to detect aspiration during swallowing.
- c) There are no documented complications of voluntary cough spirometry or pulmonary function testing.
- d) While RST has been safe and well-tolerated in a variety of patient populations, there is a chance it could result in dizziness, lightheadedness, fatigue, or shortness of breath.

**Potential Benefits:** Subjects may potentially benefit from participation through improved breathing, cough, and/or swallowing function. Participating in this study will also include an instrumental swallowing evaluation following surgery and may lead to the early identification of any swallowing impairments to minimize adverse effects of swallowing difficulty and to initiate preventative measures for risk of choking, respiratory difficulty and/or pneumonia post-operatively. Additionally, study participation may lead to sooner oral intake of food, liquids, and medications while in the hospital as a result of comprehensive swallowing testing being performed post-extubation.

**Conflict of Interest:** There is no conflict of interest to disclose for any study team member that is specifically relevant to this study.

**Summary and Conclusions:** This pilot study represents the first examination of the feasibility, safety, and physiologic impact of a targeted preoperative RST program in a small group of high-risk CS patients to prevent postoperative dysphagia and associated adverse outcomes. By carefully examining detailed aspects of physiology and health-related outcomes in a feasible design for this grant mechanism, the PI will collect high quality data to support her K99-R00 NIH grant application. These preliminary data will further inform future intervention paradigms in this challenging patient population where there is no current standard of care or evidence guided intervention guidelines for either pre or postoperative dysphagia management.

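### Aim 1's only success statement is unquantified for adherence and all-or-none for attendance and adverse events, with no intervals planned; the daily log also leaves the first relatedness judgement to the patient

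*Combined protocol and SAP*

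**What the plan says.** The Sample size justification describes the study as a pilot "to determine primarily safety and feasibility data to determine whether a large-scale clinical trial is warranted", and Specific Aims makes support for later large trials conditional on the hypotheses being confirmed.

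For Aim 1, the operational form of the hypothesis is under Aim 1 Outcomes: the training will be safe, tolerated and feasible "as measured by high adherence to RST, attendance at all telehealth/in-person sessions, and no reported adverse events". No number is attached to high adherence.

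The Aim 1 analysis reads: "Attendance, RST adherence, and adverse events will be summarized descriptively with frequency counts and percentages". Table 9 gives the measures as "RST reps completed /# prescribed, # sessions completed /# scheduled, Adverse events". Neither place names an interval or a level against which the percentages will be read.

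Adverse events reach the study by several routes:
- Under Training Logs, patients complete a daily log, among other things "to note any adverse events related to RST".
- At telehealth sessions and at the mid-point in-person visit, staff meet the patient "to complete a safety and adverse event check".
- The Data Safety Monitoring Plan adds: "Data safety monitoring will occur during weekly meetings to review Adverse Events (AE) and Protocol Deviation Logs with the PI and study team". The same section provides for medical oversight.

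Potential Risks says of the training that "there is a chance it could result in dizziness, lightheadedness, fatigue, or shortness of breath". The documents describe no procedure for assigning relatedness.

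**The concern.** A pilot meant to inform the decision on a larger trial needs results that can be read. Two of the three elements of the Aim 1 statement are absolute, and the third has no number. Taken as worded, one missed session or one reported event contradicts the hypothesis, even in a programme that runs well. Conversely, no events among 25 patients would agree with the hypothesis while leaving a material risk open. Without an interval, nothing in the planned summary would show that.

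The second issue is the log. Dizziness, lightheadedness, fatigue and shortness of breath are the effects the protocol expects the training might cause, and heart disease may also cause them in patients awaiting cardiac surgery. A log worded for training-related events asks the patient to settle cause before writing the entry. If a patient puts a training effect down to the heart condition, that source will miss it.

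**Working it through.** The plan states no precision, power or threshold for Aim 1, so there is no figure of its own to reproduce.

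**Inputs from the protocol**
- 25 patients, one group (Participants).
- Target duration 4 weeks, varying with the surgery date (RST Program).
- One to five telehealth sessions per week (Telehealth Sessions) and one in-person visit (In-Person Visit).
- At one telehealth session per week for 4 weeks: 4 + 1 = 5 sessions per patient, and 5 × 25 = 125 in all.

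**Assumed inputs.** The documents give neither attendance nor event rates, so ranges are used: per-session attendance p of 95% to 99%, and per-patient event risk r of 1% to 10%.

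**Step 1. Probability that every session is attended**

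If sessions are independent, the probability is p^N, where N is the total number of sessions. If misses cluster within patients, I used a beta-binomial with an assumed correlation of 0.3. Then a + b = 1/0.3 − 1 = 2.333 and a = 2.333p. The probability that one patient attends all 5 is the product over i = 0 to 4 of (a + i)/(2.333 + i), which is then raised to the power 25.

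| Per-session attendance | Independent, p^125 | One patient attends all 5, clustered | All 25 patients, clustered |
|---|---|---|---|
| 99% | 28% | 0.970 | 47% |
| 98% | 8% | 0.941 | 22% |
| 95% | 0.2% | 0.856 | 2% |

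Programme length and session frequency matter. If every programme lasted 2 weeks (2 + 1 = 3 sessions, 75 in all), the independent figures are 47%, 22% and 2%. At the maximum telehealth frequency for 4 weeks (20 + 1 = 21 sessions, 525 in all), 99% attendance gives 0.5%.

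**Step 2. Probability of no events, and what no events would show**

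P(no patient with an event) = (1 − r)^25:
- r = 1%: 0.99^25 = 78%
- r = 5%: 0.95^25 = 28%
- r = 10%: 0.90^25 = 7%

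The exact (Clopper-Pearson) two-sided 95% upper limit for 0/25 is 1 − 0.025^(1/25) = 13.7%. For 1/25 it is 20.4%.

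So at a true risk of 5%, the no-event outcome still occurs in more than a quarter of such studies, and the outcome itself does not exclude a risk of 13%.

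**Step 3. The routes for adverse events, side by side**

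| Route | Who records or reviews | Limited to training-related events? |
|---|---|---|
| Daily log | Patient | Worded that way |
| Telehealth check | Research speech-language pathologist | No |
| Mid-point visit check | Study team member | No |
| Weekly review of event logs | Investigator and team | No |

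The patient's attribution acts on one of four routes. How many symptoms missing from the log the other three would recover is not stated and cannot be derived from the documents. I therefore put no number on an under-count.

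**The case against.** **It is only a hypothesis.** The outcomes are analysed as counts and percentages, so a missed session would appear as a percentage below 100, not as a failed study. The protocol calls the study exploratory and intends to examine safety again in a larger cohort. This is fair. A reader might infer that Aim 1 sets a pass/fail or stopping rule; it does not. What stands is that no other Aim 1 criterion exists, and that Specific Aims ties the next step to the hypotheses being confirmed.

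**A pilot needs no power calculation.** Agreed, and none is asked for. Declining power does not remove the need to show precision for the main outcomes. A reader could compute an exact interval from patient-level counts, but the plan does not promise counts in that form.

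**The log is not the whole safety system.** This also stands. A reader might infer that the study captures only events that patients themselves blame on the training, or that the log wording loses a calculable share of events. The documents support neither. The log wording does not say that other events are to be left out, the staff checks and weekly review are not restricted to related events, and some symptoms left off the log may truly be cardiac.

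**The ratios might be pooled.** Table 9 does not state the unit, and pooling would give little weight to patients with short preoperative windows. But Training Logs has repetitions totalled for each participant, and nothing in the documents indicates pooling. Stating the unit is a clarification, not the correction of an error.

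**Conclusion.** The concern holds in this limited form. The only operational Aim 1 statement combines an undefined adherence level with two absolutes, and no intervals are planned. Read as worded, it would probably be contradicted by a programme with 98% to 99% attendance per session: the chance of full attendance is 8% to 28% if sessions are independent, and 22% to 47% with the assumed clustering. It could also be met, on events, at a risk that matters: zero in 25 has probability 28% at a true risk of 5%, and its upper limit is 13.7%. The attendance figures rest on assumed rates, 5 sessions per patient and, for clustering, an assumed correlation of 0.3. The 13.7% limit depends only on n = 25 and would be higher with fewer evaluable patients.

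The log wording is a lesser, separate weakness in one of several event sources. It is worth correcting because the symptoms at issue are the expected ones, but its effect on the event count is unknown. The trial can run as written; what suffers is the reading of its primary result.

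**What to change.** 1. **Success statement and analysis** (Aim 1 Outcomes; Statistical analyses, Aim 1; Table 9). Replace the absolutes with per-patient proportions among all who start training, using Table 9's ratios over each patient's actual preoperative window: patients who complete at least a stated share of prescribed repetitions, and patients who attend at least a stated share of scheduled sessions. Report exact 95% intervals. Before enrolment, the sponsor should fix the repetition share, the attendance share and the proportion of patients against which results will be read. To show what 25 patients can support, 20/25 has an exact interval of 59.3% to 93.2%. State in the plan that 0/25 events is compatible with a risk up to 13.7%.

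2. **Adverse events** (Training Logs, staff checks, Data Safety Monitoring Plan). Have the log and staff checks record any new or worsened symptom during the training period regardless of cause. Assign relatedness at the existing weekly review under medical oversight. Report all-cause and training-related events as the number of patients with at least one, with exact intervals.

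**Cost.** Wording changes in the protocol, log and Table 9; three pre-stated numbers; more event entries to classify each week, in a number the documents do not allow us to estimate; and a less absolute safety statement. No extra visits, staff or patients.

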#### **Research Evaluation 2:**

After completing the RST program and prior to surgery, CS patients will undergo PFTs, read the bamboo passage, and complete the LCADL as they did during Research Evaluation 1. Additionally, they will undergo a standardized Fiberoptic Endoscopic Evaluation of Swallowing (FEES). The second research evaluation will take approximately 45 minutes to complete.

Fiberoptic Endoscopic Evaluation of Swallowing (FEES): CS patients will undergo a FEES exam in a dedicated room (UB 1707, UB 1739) in the preoperative clinic or the ARC lab before and after the RST program using an Olympus flexible video HD Rhino Laryngoscope (ENF-V3) connected to a portable video processor and light source (Olympus CV170). To ensure patient comfort, a water-soluble lubricant (Aplicare sterile lubricating jelly 82-280) and, per participant preference, a topical numbing-agent (i.e., lidocaine hydrochloride jelly USP, 2%) will be applied to the nares, and the laryngoscope will be passed trans-nasally through the nasopharynx and hypopharynx until an optimal position is obtained. The topical numbing agent will be used per participant preference and pending physician authorization.

During laryngoscope advancement, the participant may be asked to hum or say “eeeeee” to help visualize anatomy and placement of the laryngoscope. A standardized FEES protocol will be used that includes a combination of voicing and swallowing tasks. Once optimal scope positioning is confirmed, the participant will be asked to perform a series of voicing tasks to allow assessment of laryngeal and vocal fold movement that include: 1) sustained vowel “ah” 2) vowel/sniff alternating task; 3) cheek puff task; 4) breath hold task; and 5) a pitch glide of the vowel “e”. CS patients will be given 5mL Gatorade x2, 10mL Gatorade x2, comfortable cup sip x2, teaspoon pudding x2, cracker x2, and M&Ms x3. A liquid that is colored needs to be used so that it may be visualized during swallowing. Gatorade will be the typical option but if a participant has dietary restrictions or a dislike for Gatorade other options will include grape juice or milk. To ensure patient safety, swallowing trials will be discontinued after two episodes of gross aspiration or if a patient is unable to clear >70% of the bolus. At the completion of the swallowing trials, the laryngoscope will be carefully removed.

Recordings will be saved on a USB200 recording device with an encrypted hard drive. The FEES images will be labeled with the participant identification study number and immediately transferred onto the Aerodigestive Research Core laboratory server to ensure data is not lost. This is a secure server and only individuals within the lab included on this IRB will have access to saved and coded files. The video images will remain on the encrypted hard drive until the end of the study and then they will be deleted. The transferred recordings will be kept on our secure server for five years following the completion of the study. Additionally, if abnormalities are noted that would be pertinent to the participant’s medical care (for example, vocal fold paralysis or aspiration), our study team will alert the medical team (attending physician or nurse caring for the participant) that an abnormality was detected.

